8. STUDY OBJECTIVES

Primary Objectives

- (1) To determine the preferred recruitment venue and testing modality that targets and finds the highest number of HIV infected and at risk female youth aged 15-24 years in Homa Bay County, Nyanza region, western Kenya. This will be determined by examining uptake and yield of previously undiagnosed HIV infection of the two 'seek' strategies (community or home-based) and the three 'test' strategies (self-testing, HTS in a mobile/home setting, or facility-based HTS) among female youth;
- (2) To conduct an economic evaluation, using cost effectiveness analyses to determine the relative utility of each seek, test, link, and prevention intervention.

Secondary Objectives

- (1) To pilot and evaluate an adaptive intervention to link newly diagnosed HIV-positive female youth to treatment and care services;
- (2) To identify barriers and facilitators to seeking HIV care services after receiving a positive diagnosis;
- (3) To identify barriers and facilitators to seeking HIV prevention services for high risk female youth after receiving a negative HIV test result;
- (4) To provide an HIV prevention intervention to a randomly selected subset of high-risk negatives (motivational text message with referral for combination prevention interventions), and to re-test them at 12 months.

9. STUDY DESIGN

9.1 Description of the Study Design

The GIRLS study will rigorously compare two 'seek' recruitment strategies, three 'test' strategies, and two enhancements to an adaptive (SMART trial design) 'linkage' to care intervention, among young at-risk women, 15-24 years old, in Homa Bay County, western Kenya. Additionally, we will evaluate a scalable primary prevention messaging intervention to support identified high risk HIV-negative young women in reducing HIV risk and adhering to recommended HIV re-testing recommendations. This study design will allow us to follow participants along both the prevention and care continua. Figure 3, summaries the study design.

[figure not shown]

Figure 3: Study Design

10. STUDY POPULATION

10.1 Description of Study Site and Study Population:

The study will be carried out in Homa Bay County, Nyanza region, western Kenya. HIV is a major crisis in Nyanza with ages 15-64 having an HIV prevalence of 15.1% compared to national prevalence of 5.6% (NASCOP, 2014a). Homa Bay County has a total population of 1,053,465 and has the highest prevalence of HIV in Kenya, at 25.7% (NASCOP, 2014b). In addition, prevalence is higher among women (27.4%) than men (23.7%). Despite this high prevalence and the importance of HIV testing for prevention and treatment, 31% of people in Homa Bay still had never tested for HIV by 2009 (NASCOP, 2014b). High fertility, early coitarche, frequent intergenerational sex and low male circumcision put many young women at increased risk for HIV infection. It is therefore critical to prioritize access to HIV testing, prevention, and treatment for this population. This study will be conducted among female youth 15-24 years old (the highest risk age group).

10.2 Target sample size

We project to reach 1,200 female youth over an accrual period of up to 12 months, plus one year of follow-up. Therefore, in order to stay within the estimate 12 months of recruitment, we will put in place adequate field staff during the implementation phase of the project.

Because Aim 1 of this study is not a clinical trial, but rather an exploration of differences in the yield of previously undiagnosed HIV infection across recruitment and testing strategies, we started with this large and feasible sample size and conducted power calculations to determine the size of effects detectable with at least 80% power. By recruiting 1200 female youth between the age of 15-24 years, we will have 80% power to detect an odds ratio of 1.67 when comparing recruitment strategies, on the proportion of previously undiagnosed female youth testing positive for HIV infection. And when comparing testing approaches within a recruitment strategy on that same outcome, an odds ratio of 2.01 can be detected with 80% power. These calculations, which are presented in more detail in section 15.11, show the proposed sample size (N=1200) is capable of detecting modest differences in the yield of previously undiagnosed HIV infection across both recruitment strategies and testing approaches.

We expect large numbers of youth to participate through both venues (IRDO reaches tens of 1000s of youth/year). Based on our experience with MP3 Youth (data not yet published) study (KNH/UON ERC P23/03/2011), which screened N=788 female youth and enrolled N= 690 female youth over a period of 8 months (November 19, 2014 – June 12, 2015) in the same county, we anticipate that we will be able to recruit 1,200 females over a period of 12 months with enhanced recruitment effort. We expect the sample accrual rate to be slower than in MP3 Youth, because we will be recruiting only female youth and mainly those out of school (a large proportion of younger MP3 Youth girls were in school and easier to recruit). In addition, we have two different recruitment strategies, and the home-based strategy may be more labor intensive and time consuming than a community mobile event. We therefore expect a somewhat lower accrual rate.

The sample size for the linkage to care adaptive intervention pilot is an estimate of the number of female youth with previously undiagnosed HIV infection we anticipate reaching. The expected percentage of girls testing positive was based on our MP3 Youth pilot study (data not yet published), and we expect 9% of all tested girls to have HIV infection not previously diagnosed. Thus given a total sample size of 1,200 female youth, we anticipate enrolling about 108 previously undiagnosed HIV positive females in the adaptive intervention pilot to link HIV positive female youth to HIV treatment and care.

Sampling method: We will stratify the sample by conveniently selected sub-counties; Homa Bay municipality, Mbita sub-county and Ndhiwa sub-county. Mapping of catchment areas surrounding health facilities will be used to establish relationships with referral clinics. We select a random starting point that is within walking distance (about 5km) of the catchment area of the health facility. Approximately four hundred (400) participants will be recruited from each stratum and for each stratum it is assumed that 200 participants will be recruited through each recruitment approach. Both recruitment strategies (household and mobile event) will run concurrently until the desired sample size is reached. If needed for sample size attainment, we will expand the sampling area to a 6 - 10 km circumference of the referral clinic.

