11.3 Eligibility Determination (Inclusion/Exclusion) and Enrollment

Participants will be screened for eligibility by Research Assistants or other study staff. Participants must meet all inclusion criteria and may not meet any exclusion criteria in order to be eligible to participate in the study.

Eligibility Requirements:

Inclusion Criteria:

- Female between the ages of 15-24.
- Able to understand spoken English or Kiswahili or Dholuo.
- Resides in Homa Bay County.
- Not previously diagnosed as HIV positive.
- Willing to give informed consent or if younger than 18 years of age and not an emancipated minor, has a parent or guardian willing to provide consent in addition to the minor's assent.

Exclusion Criteria:

- Male.
- Unable to understand spoken English, or Kiswahili or Dholuo.
- Females who are older or younger than the ages of 15-24.
- Resides outside of Homa Bay County.
- HIV positive.
- If under 18 and not an emancipated minor, unable to get parental consent.

Enrollment

After eligibility is assessed/confirmed, participants will be offered enrollment using the approved recruitment script. If she agrees, she will be taken through the following study enrollment procedures: (1) completing registration (to generate a study ID and to ensure single enrollment); and (2) completing the baseline behavioral survey using the tablet computer. Once enrolled, the participant will choose her preferred HIV testing options: (1) oral fluid HIV self-testing at her convenience, (2) HIV testing services (HTS) by study staff at the recruitment location, or (3) a referral to a health care facility for standard HTS. Participants who elect self-testing will be given the self-test kit and will be taken through the self-testing counseling using visual aids (either in the home or in the community). For participants who select staff administered HTS, the test will be conducted by the study staff. For participants who request a referral for HTS at a health facility, they will be given a referral card with the name of a staffer (or other contact to be determined) at the facility. All participants will complete the participant assessment tracking form (this includes locator information for follow-up).

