Logistic regression analysis will be used to determine which recruitment and HIV testing approaches yield the highest proportion of newly diagnosed HIV infection. HIV testing result (negative vs. positive) will be regressed on variables indicating recruitment strategy (home vs. community) and type of HIV testing (self, staff-aided, facility-based). With facility-based testing following community-based recruitment as a reference category, we will estimate how home-based recruitment and other testing approaches change the odds of a positive test result. The interaction between recruitment strategy and HIV testing approach will be tested to determine whether the yield of each testing approach is conditional on recruitment strategy. If a significant interaction effect is found, simple main effects of testing approach within each recruitment strategy and simple main effects of recruitment strategy within each testing approach will be estimated. In addition to comparing yield by recruitment strategies and testing approaches, we will consider interaction effects with youth characteristics, such as age, risk behaviors, and HIV testing history, and type of testing. Similar logistic regression analyses will examine differences in the odds of completing all confirmatory testing by recruitment strategy and approach to testing.

Home-based and community-based recruitment strategies will also be compared to determine which strategy is more effective in reaching higher risk female youth. Rates of acceptance of screening among potential participants offered screening and rates of enrollment among eligible participants will be compared by recruitment strategy using logistic regression. Risk will be characterized by number and serostatus of sex partners, concurrency, condom use, and patterns of HIV testing by the participant and any sex partners.

A random selection of N≈185 girls with HIV negative tests will be followed-up. We will assess risk behaviors, condom use, additional HIV testing, linkage to prevention and any new HIV diagnoses over the year since study enrollment. Re-testing, prevention service use, and new HIV will be examined in relation to recruitment strategy, testing approach at enrollment, and participant risk behavior and other characteristics.

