With this estimate of the expected percentage of girls with newly diagnosed HIV infection, we asked how small of an increase in the odds of newly diagnosed HIV infection could be detected with 80% power when community-based recruitment is compared to home-based recruitment. With 600 youth recruited by each strategy, power is 80% to detect an odds ratio of 1.67, in other words, a modest increase from 9% to 14% newly diagnosed with HIV infection. When comparing testing approaches, and assuming an equal proportion of girls prefers each approach and testing approach does not interact with recruitment strategy, power is 80% to detect an odds ratio of 1.85. If there is an interaction between recruitment strategy and testing approach, when comparing

testing approaches within a recruitment strategy (i.e., estimating simple main effects), power is 80% to detect an odds ratio of 2.32.

These calculations show the proposed sample size (N=1200) is capable of detecting modest differences in the yield of newly diagnosed HIV infection across both recruitment strategies and testing approaches.

Among the approximately 108 female youth we expect to be newly diagnosed with HIV infection, about 20% are expected to successfully initiate HIV care at a health facility after a single SMS message. The remaining 80% (N=86) who are not linked to care after the initial SMS message will be randomly assigned to either continued SMS messages or to economic incentives. Assuming at least 60% are linked to care at some point during follow-up, survival analysis employing Cox regression will be able to detect a hazard ratio of 2.2 describing the impact of treatment condition (continued SMS vs. economic incentives) on the occurrence and timing of successful linkage to care at a health facility, with 80% power.

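### Section 10.2 gives a detectable odds ratio of 2.01 for testing approaches within a recruitment strategy, but section 15.11, which it cites for the detail, gives 2.32

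*Combined protocol and SAP*

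**What the plan says.** Section 10.2 (Target sample size) fixes N at 1200 and reports the effects that this number can detect for newly diagnosed HIV infection. It gives an odds ratio of 1.67 between recruitment strategies. For the testing options it says: "when comparing testing approaches within a recruitment strategy on that same outcome, an odds ratio of 2.01 can be detected with 80% power". It then names its source: "These calculations, which are presented in more detail in section 15.11".

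Section 15.11 (Sample Size Considerations, Power Analysis) gives three odds ratios for Aim 1:

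- Between recruitment strategies: "With 600 youth recruited by each strategy, power is 80% to detect an odds ratio of 1.67".
- Between testing approaches with no interaction with recruitment strategy: "power is 80% to detect an odds ratio of 1.85", on the basis of "assuming an equal proportion of girls prefers each approach".
- Within a strategy, if there is an interaction: "testing approaches within a recruitment strategy (i.e., estimating simple main effects), power is 80% to detect an odds ratio of 2.32".

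The two sections agree on 1.67. They disagree on the within-strategy figure.

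**The concern.** Both sections describe one calculation: the same comparison, outcome, power and total sample. One of the two figures must therefore be wrong or mislabelled, and 10.2 does not match the section it cites.

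The comparison is part of the planned analysis. Section 13.2 says: "If a significant interaction effect is found, simple main effects of testing approach within each recruitment strategy" will be estimated, and testing modality is part of the first primary objective. Because N was set first, the detectable effect is the only product of the power analysis. Someone who reads only 10.2 would take the study to have 80% power for a rise from 9% to 16.6% within a strategy. If that power is not there, a null within-strategy result could be over-read as evidence against an odds ratio near 2.

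**Working it through.** **Inputs**

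- Reference proportion p1 = 0.09 (15.11, rounded from 55/636 = 8.65%).
- 600 girls per recruitment strategy (15.11).
- Three testing approaches in equal shares: 1200/3 = 400 per approach overall and 600/3 = 200 within a strategy. Section 15.11 states equal shares in its no-interaction sentence. I infer that they carry over to the within-strategy figure.
- Two-sided alpha 0.05. This is an assumption, since the documents give no alpha for Aim 1.

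**Method.** For odds ratio OR, p2 = OR·p1 / (1 − p1 + OR·p1). With n per group and p̄ = (p1 + p2)/2,

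power = Φ{ [ (p2 − p1) − 1.96·√(2p̄(1 − p̄)/n) ] / √(p1(1 − p1)/n + p2(1 − p2)/n) }.

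This pooled two-proportion test gives the same results as the standard logistic-regression formula for a binary covariate.

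**Step 1: reproduce section 15.11**

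| Comparison | n per group | OR in 15.11 | p2 at that OR | Power at that OR | OR at 80% power |
|---|---|---|---|---|---|
| Recruitment strategies | 600 | 1.67 | 14.2% | 80.0% | 1.670 |
| Testing approaches, no interaction | 400 | 1.85 | 15.5% | 79.8% | 1.852 |
| Testing approaches within a strategy | 200 | 2.32 | 18.7% | 80.2% | 2.317 |

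One set of inputs returns all three figures to two decimals. That supports both the assumed alpha and 200 per approach.

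**Step 2: test 2.01 on the same inputs**

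- p2 = 2.01 × 0.09 / (0.91 + 2.01 × 0.09) = 0.1658; p2 − p1 = 0.0758; p̄ = 0.1279.
- With n = 200 the null standard error is 0.0334 and the alternative standard error is 0.0332.
- Power = Φ[(0.0758 − 1.96 × 0.0334)/0.0332] = Φ(0.31) = 62.3%.
- The unpooled formula gives 62.7%, the Wald test on the log odds ratio 61.0%, and a simulated likelihood-ratio test (200,000 replicates) 63.0%.
- For 80% power at 2.01 the pooled formula needs 304 girls per approach (301 to 313 across formulas).

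**Step 3: look for an input that gives 2.01**

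- One-sided 0.05: detectable OR 2.13 at 200 per group. It also turns the agreed 1.67 into 1.58.
- Reference 55/636: detectable OR 2.34; power at 2.01 is 60.8%.
- Bonferroni alpha for three pairs (0.05/3): detectable OR 2.59.
- 300 per group: detectable OR 2.017 pooled or 2.011 unpooled; power at 2.01 is 79.6% pooled. This would be a strategy's 600 girls split between two approaches instead of three. It is close to 2.01, but the documents do not say that it is the origin.

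**Step 4: unequal uptake.** Section 11.3 says: "Once enrolled, the participant will choose her preferred HIV testing options". The splits below, for two approaches within one strategy, are illustrations and do not come from the documents.

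| Split | Detectable OR | Power at 2.01 |
|---|---|---|
| 290 vs 290 | 2.04 | 78% |
| 240 vs 240 | 2.17 | 70% |
| 100 vs 480, larger group at 9% | 2.40 | 60% |
| 100 vs 480, smaller group at 9% | 2.56 | 48% |

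**The case against.** The best counter-argument concerns weight. Aim 1 is described as an exploration and not a clinical trial, a feasible N was chosen first, and nothing was derived from 2.01. Section 15.11 already carries the larger figure, so a reader who follows the cross-reference is not misled. The within-strategy analysis is run only if the interaction is significant. All of this is true. It limits the damage to a misstated detectable effect, but it does not make 2.01 consistent with 15.11.

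The 62% also rests on inference. Alpha is unstated, 200 per group is never written out, and the figure is for a pairwise comparison. Setting one approach against the other two combined (200 vs 400, the larger group at 9%) gives a detectable odds ratio of 2.07 and 76.5% power at 2.01. This too falls short of 80%, and the reference-category model in section 13.2 points to pairwise comparisons.

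The suggestion that 2.01 came from 300 per group is weak as well. The pooled formula, which returns 15.11's figures, gives 2.02 at 300 after rounding. The unpooled formula gives 2.01 at 300 but 2.31 (2.305) at 200, not 2.32. The origin of 2.01 should be treated as unknown.

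**Conclusion.** The concern holds. That the two sections contradict each other needs no assumption. On which figure is right, 2.32 follows from 15.11's inputs and 2.01 does not. Assuming 9% in the reference group, 200 girls per approach and two-sided 0.05, the odds ratio detectable with 80% power is 2.32 (2.30 to 2.36 across variance formulas), and power at 2.01 is about 62% (61% to 63%). Realised power will depend on which tests the girls choose. N=1200, the 1.67 for recruitment strategies and the planned analyses are unaffected. It should be fixed, with high confidence.

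**What to change.** First confirm with whoever ran the power calculation that 2.01 was not meant for a different, two-group comparison. If it was, label it as such and give its group sizes. Otherwise replace 2.01 in section 10.2 with 2.32 (9% to 18.7%), and state that the figure assumes equal preference for the three approaches and which alpha was used. The alpha should also be entered in 15.11. Adding the no-interaction figure of 1.85 to 10.2 is optional.

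The cost is a sentence or two of wording. The sample size, design and analyses do not change.

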11. STUDY INTERVENTIONS

11.1 Recruitment

11.1.1 Recruitment strategy

We will work in partnership with the local community in conjunction with IRDO, our implementing partner. IRDO, has already successfully delivered combination HIV prevention services to youth in many counties in Nyanza, and most recently completed an HIV prevention study (MP3 Youth; R01AI094607; DAIDS Protocol Number 11989).

Point of Entry:

Local Mobilizers (Liaisons): Existing community mobilizers (outreach workers), who are affiliated with the implementing partner, will be the project liaisons for community entry. The individuals will facilitate meetings between the project staff and the local authorities (chiefs, community representatives, youth leaders, and health authorities). Community entry will begin by contacting local mobilizers who are well established in the target area through their established HTS efforts.

Community Meetings: The study staff will request the local authorities for permission to participate in *barazas* (community meetings) or other organized community meetings where they will present the objectives of the study using a study-specific IRB-approved recruitment flier in an effort to sensitize the community to the study and to obtain the community's permission to proceed with conducting the study.

Meeting with Local Chief: In cases where there are no local mobilizers, the field site PI, field site coordinator, and study staff will first request a meeting with the respective chiefs of each site. The chiefs will then direct the study staff to the appropriate local partners (community representatives, youth leaders, and health authorities).

Community Advisory Boards: We have identified community stakeholders in each of the study sites to engage as members of community advisory boards (CABs). We will form three CABs, one for each site. The CABs will act as the link between the study and the community/participants. We will train them on the study to enable them to address issues that could arise about the study in the community, or to contact study staff where needed. Given their vast knowledge of the study population and communities, the CAB members will review and give input on our recruitment strategies before we start and on an ongoing basis.

Community Recruitment: The following areas were identified by female youths during the formative research phase of the MP3 Youth study (data not yet published) as venues where they would like to receive HIV testing services: (1) markets, (2) schools, (3) community organizations, non-governmental organizations, (4) community social events, (5) health facilities, and/or (6) churches. Therefore, these venues will serve as the sites for the community-based recruitment, where mobile health tents will be set up. Study staff will identify an appropriate location to set up

the mobile tents that will ensure that study procedures can be conducted while protecting participant confidentiality. Information on other recruitment sites and approaches will be obtained from CAB members and study recruiters hired from the same communities.

Home Based Recruitment: Households will be included if there is a female 15-24 years of age. Participants will be identified in their homes. RAs/Counselors/Study Staff will ensure that any other family members in the home understand the study is focusing on females, but the RA will be trained to make referrals for any other issues that he/she identifies within the home.

Home-based and community-based recruitment will be carried out by GIRLS study staff, who will offer participation to a potential participant by reading them the IRB-approved **recruitment script**. If a potential participant declines to participate, they will be asked to fill out a refusal survey and thanked for their time. If willing to participate, they will be given a flier and if recruited via the community-based strategy will be directed to or taken to the mobile study tent area for IC. If recruited via the home-based strategy, they will undergo IC in a private area in their household. All participants will be informed that they will be contacted in 2 weeks in order to complete an SMS survey about their HIV testing experience.

Offer of Participation

IRB approved fliers will be used to recruit participants. The fliers will be distributed and posted in areas frequented by female youth (15-24), such as (1) markets, (2) schools, (3) community organizations, non-governmental organizations, (4) community social events, (5) health facilities, and/or (6) churches.

All potential participants who are approached will be documented on the participant assessment tracking form. If the individual agrees to participate, then study staff will explain about the study and proceed with IC, eligibility determination, and registration.

Individuals who do not consent/or withdraw consent, or who do not meet the study eligibility criteria will not be enrolled in the study but will receive onsite provision of standard services provided by IRDO program (not study) staff and referrals for whatever other services they request

